## **Study Protocol**

### **Title**

The Effect of Intra Aortic Balloon Pump Early Insertion on Mortality in Post Cardiac Arrest Patients with Acute Coronary Syndrome

### **Sponsor**

Indonesia University

### **Aim**

To observe the effects of intra aortic balloon pump on clinical outcomes of cardiac arrest patients and prognosis improvement through circulation and tissue perfusion improvement.

### **Study Design**

Randomized clinical trial.

### **Anticipated Outcome**

Early insertion of intra aortic balloon pump will be improving in-hospital mortality rate of cardiac arrest patients with acute coronary syndrome.

### **Inclusion and Exclusion Criteria**

#### **Inclusion Criteria**

1. Cardiac arrest survivor patients with acute coronary syndrome
2. Age over 18 years and less than 75 years

#### **Exclusion Criteria**

1. History of stroke based on anamnesis
2. Unequal pupil
3. History of previous intra aortic balloon pump usage
4. Aortic regurgitation
5. Brugada and congenital long QT syndrome

### **Withdrawal or Discontinuation Criteria**

1. Patient dies prior to intra aortic balloon pump insertion
2. Treatment termination requested by family
3. Anemia due to hemorrhage with a decrease in Hb > 3 g / dL
4. Ankle brachial index (ABI) less than 0.8

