### **Procedures**

1. Patients who meet the criteria and agree to participate in the study taken as the subject of the research.
2. Research subjects were then randomized into two groups. The control group (Group A) and the treatment group (Group B) as the group that receiving intra aortic balloon pump (IABP) as early as possible within 3 hours after the return of spontaneous circulation (ROSC). IABP insertion is performed by an interventionist.
3. Baseline data such as age, weight, height, risk factor (hypertension, Diabetes Mellitus,

dyslipidemia, smoking, family history), history of Acute Myocardial Infarct (AMI), Percutaneous Coronary Intervention (PCI), Coronary Artery Bypass Graft (CABG), and valvular disease will be taken. Vital signs examination and EKG 12 leads will be performed.

- Laboratory tests for peripheral venous blood include: Lactate levels, urea (Ur), creatinine (Cr), n-terminal pro B-type natriuretic peptide (NT Pro BNP), high sensitive troponin (Hs Trop), IL-6, beclin 1 and caspase 3.
  - Central venous blood examination for central venous blood gas analysis includes assessment of a-vO2 diff and ScvO2.
  - Arterial blood examination for arterial blood gas analysis.  
Monitoring of hemodynamic parameters using echocardiography machines (ejection fraction, TAPSE, cardiac output, VTI).
4. In the group B, IABP is initiated within 3 hours after the return of spontaneous circulation by the interventionist.
  5. Blood sampling is repeated at 6th hour post ROSC or 1 hour post-insertion of IABP consisting of:
    - Laboratory tests for peripheral venous blood include lactate, IL-6, beclin-1 and caspase 3 levels.
    - Central venous blood examination for central venous blood gas analysis includes assessment of a-vO2 diff and ScvO2.
    - Arterial blood examination for arterial blood gas analysis.  
Examination of hemodynamic parameters with echocardiographic machine was repeated at the 6th hour post ROSC, consisting of ejection fraction, TAPSE, cardiac output, VTI).
  6. Research subjects will be monitored during hospitalization.

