### **Analysis Method**

Data analysis using SPSS 20.0 software program with appropriate statistical test. Data taken during the study will be displayed according to the variable type. Numerical variables with normal distribution will be displayed as mean  $\pm$  standard deviation, which is then analyzed by a general linear model (GLM) test for data measured more than once (IL-6, Beclin-1, Caspase-3, a- vO2 diff, and ScvO2) and independent t test for data with one time measurement (mortality rate in hospital and effective lactate clearance). Numerical variables with abnormal distribution will be shown in median (minimum-maximum) and then analyzed by Mann-Whitney test. The categorical variable will be displayed as a percentage (number) and will be analyzed by chi-square test or alternate test.

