### **Primary Outcome**

In-hospital mortality

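### Withdrawing patients who die before balloon pump insertion takes primary-outcome deaths out of the IABP arm only

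*Combined protocol and SAP*

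**What the plan says.** The primary outcome is "In-hospital mortality". Four parts of the combined protocol and SAP bear on which deaths are counted.

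- **Procedures, item 2:** "Research subjects were then randomized into two groups", control (Group A) and early IABP (Group B). Baseline data, blood samples and echocardiography follow in item 3.
- **Procedures, item 4:** "In the group B, IABP is initiated within 3 hours after the return of spontaneous circulation by the interventionist". No insertion is planned for Group A.
- **Withdrawal or Discontinuation Criteria, item 1:** "Patient dies prior to intra aortic balloon pump insertion".
- **Analysis Method:** a categorical variable "will be analyzed by chi-square test or alternate test". The section names no analysis population, has no intention-to-treat statement, and gives no rule for patients who were withdrawn.

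**The concern.** Randomisation comes before insertion, so there is an interval in which a Group B patient can die without a pump. Such a patient has already had the primary outcome event, and the withdrawal rule is triggered by that same event. Group A has no planned insertion and no matching time window, so an identical early death there remains an event.

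This is immortal-time bias: to stay in Group B a patient must survive to insertion, while no such condition applies in Group A. It breaks the comparability that randomisation provides, on the primary endpoint, and in favour of the result given under Anticipated Outcome. None of the listed tests corrects it. A larger trial estimates the wrong quantity more precisely, so the false-positive rate rises with sample size.

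**Working it through.** The document gives no event rate, sample size, significance level or power, so there is no stated figure to reproduce. The check asks what the rule does when IABP has no effect.

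**Inputs**
- From the document: randomisation before insertion; insertion planned in Group B only; binary primary outcome; death before insertion is a withdrawal.
- Assumed: true mortality m, equal in both arms, from 40% to 70%; share e of Group B dying between randomisation and insertion, from 2% to 15%; 1:1 allocation; n = 30, 50, 100 or 200 per arm; two-sided 5% test by uncorrected chi-square (pooled z test).

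**Bias**
1. Group A mortality is m.
2. Group B loses e from both numerator and denominator: (m − e)/(1 − e).
3. Spurious reduction: m − (m − e)/(1 − e) = e(1 − m)/(1 − e). This is positive for every e > 0 and m < 1, so the error always favours IABP.
4. Apparent odds ratio: the Group B odds are (m − e)/(1 − m) and the Group A odds are m/(1 − m), so the ratio is 1 − e/m. Here e/m is the share of all in-hospital deaths that fall in the gap.

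Example with m = 50%, e = 10%, 100 per arm: Group A has 50/100 = 50%. Group B has (50 − 10)/(100 − 10) = 40/90 = 44.4%.

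**Chance of a false claim of benefit (nominal 2.5%)**

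Let p_B = (m − e)/(1 − e), d = m − p_B, and let the arms analysed be n and n(1 − e). The pooled rate is p̄ = (2m − e)/(2 − e). Let s0 be the standard error using p̄ and s1 the standard error using the separate rates. The probability is Φ[(d − 1.96·s0)/s1].

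For the example: p̄ = 0.90/1.90 = 0.474, s0 = 0.0726, s1 = 0.0724, d = 0.0556. So Φ[(0.0556 − 0.1422)/0.0724] = Φ(−1.20) ≈ 11.6%.

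Results at m = 50%:

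| e | Share of deaths in gap (e/m) | Apparent Group B mortality | Spurious reduction (points) | Odds ratio | n = 30 | n = 50 | n = 100 | n = 200 |
|---|---|---|---|---|---|---|---|---|
| 2% | 4% | 49.0% | 1.0 | 0.96 | 3.0% | 3.2% | 3.5% | 3.9% |
| 5% | 10% | 47.4% | 2.6 | 0.90 | 3.9% | 4.4% | 5.6% | 7.5% |
| 10% | 20% | 44.4% | 5.6 | 0.80 | 6.1% | 7.8% | 11.6% | 19.0% |
| 15% | 30% | 41.2% | 8.8 | 0.70 | 9.5% | 13.2% | 22.2% | 39.6% |

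Simulated trials agree with these probabilities to within 0.4 points where both were run.

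**Other mortality rates.** At e = 10% the spurious reduction is 6.7 points for m = 40% and 4.4 points for m = 60%. Over the whole assumed range it runs from 0.6 points (m = 70%, e = 2%) to 10.6 points (m = 40%, e = 15%).

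**Comparator.** With every randomised patient kept in the assigned arm, the expected difference is 0. The simulated two-sided error rate is then 4.8% to 5.7%, the spread coming from the discreteness of the chi-square test.

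**The case against.** The strongest reply is that removal from the analysis is inferred. The list is headed withdrawal or discontinuation, never mentions analysis, and its other items could plausibly be reasons to stop treatment; item 1 might only record that the procedure ended. It is true that the document does not say outright that these patients leave the analysis. But a patient who has died before insertion has no balloon pump treatment left to discontinue, so removal from the study is the only reading that gives the item an effect, and no other section retains these patients.

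Second, control care is undefined and later insertion in Group A is not forbidden, so it is a reading that the rule reaches Group B only. It is the natural one. Applied literally to controls who never receive a pump, the rule would withdraw every control death, which cannot be intended.

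Third, the size is uncertain, and this stands. The gap starts at randomisation, not at return of circulation, so it is shorter than 3 hours. At m = 50%, e = 10% and 15% require 20% and 30% of all in-hospital deaths to fall in it. At e = 2% the bias is about one point and the error rate barely moves. The document gives no basis for choosing among these values.

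Finally, a sentence defining the analysis population would remove the bias without deleting item 1. That is correct, but leaving the item in place would leave two conflicting instructions.

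**Conclusion.** The concern holds. Followed as written, the plan withdraws primary-outcome events from one arm and creates an apparent benefit of IABP where none exists. The direction is certain for any death in the gap, given that withdrawn patients are not analysed and that the rule operates in Group B alone. The size is conditional: 1.0 to 8.8 points at an assumed 50% mortality with 2% to 15% dying in the gap, and 0.6 to 10.6 points over the wider assumed range. The bias may be small in practice, but the plan gives no means of showing that, and a positive result could not be safely attributed to the device. This must be fixed before the mortality analysis.

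**What to change.** Delete item 1 from the Withdrawal or Discontinuation Criteria. Add to Analysis Method that:

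- the primary analysis includes every randomised patient in the assigned group, whether or not a pump was inserted and whether or not insertion fell within 3 hours;
- every in-hospital death from randomisation onward counts as a primary outcome event;
- patients meeting any of the remaining withdrawal criteria stay in the mortality analysis, because bleeding, a low ankle brachial index or family request could also fall unevenly between the arms;
- an analysis restricted to patients who received the device, if wanted, is labelled as a sensitivity analysis.

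The cost is a change of wording in two sections. No extra patients or data are needed, since the plan already states "Research subjects will be monitored during hospitalization". The estimated effect may look less favourable to IABP than under the present rule.

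### Death before pump insertion is listed as a withdrawal criterion although it is a primary-outcome event, and no analysis population says that it is counted

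*Combined protocol and SAP*

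**What the plan says.** The first of four entries under Withdrawal or Discontinuation Criteria is "Patient dies prior to intra aortic balloon pump insertion". The others are "Treatment termination requested by family", "Anemia due to hemorrhage with a decrease in Hb > 3 g / dL" and "Ankle brachial index (ABI) less than 0.8". The heading covers withdrawal and discontinuation together. It does not say which entries end the device treatment, which end study participation, and which, if any, take a patient out of the analysis.

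The order of events is in Procedures. Item 2 reads "Research subjects were then randomized into two groups". Baseline data, bloods and echocardiography follow in item 3, and item 4 reads "In the group B, IABP is initiated within 3 hours after the return of spontaneous circulation by the interventionist". No insertion is described for Group A. Item 6 adds "Research subjects will be monitored during hospitalization".

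The Primary Outcome section gives in-hospital mortality. The Analysis Method section lists tests by type of variable. It names no analysis population and does not say how patients who meet a withdrawal criterion are handled.

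**The concern.** A patient who dies in hospital after randomisation and before insertion has had the primary-outcome event. Listing that event as a ground for withdrawal invites an analyst to leave it out. On the procedures described, only Group B has an insertion to precede, so the list has no matching entry for a control who dies in the same few hours.

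If the Group B deaths were left out, observed Group B mortality would fall whatever the pump does. That is also the direction the plan expects: "Early insertion of intra aortic balloon pump will be improving in-hospital mortality rate of cardiac arrest patients with acute coronary syndrome". The error would be systematic, so enrolling more patients would not remove it.

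The remaining entries raise the same question less sharply. A haemorrhagic fall in haemoglobin or a low ankle brachial index arises after randomisation and may be caused by the pump. Item 2 leaves open whether a death after the family ends treatment is counted.

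**Working it through.** The plan gives no sample size, significance level, expected mortality or allocation ratio, so it has no figure to reproduce. The structure below comes from the documents; every numerical input is assumed.

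**From the documents**
- Outcome: death in hospital (Primary Outcome).
- Sequence: randomisation, then insertion within three hours of ROSC, described for Group B only (Procedures, items 2 and 4).
- Death before insertion is a listed criterion (Withdrawal or Discontinuation Criteria, item 1).
- Analysis population: not stated (Analysis Method).

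**Assumed**
- The pump has no effect, so true mortality is *m* in both arms.
- A share *d* of randomised Group B patients die before insertion and are removed. No one is removed from Group A.

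**Formula.** Removing *d* takes *d* from both the deaths and the patients in Group B:

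- Observed Group B mortality = (m − d)/(1 − d)
- Observed Group A mortality = m
- Spurious benefit = m − (m − d)/(1 − d) = (1 − m)d/(1 − d)

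This is positive for every d > 0 and m < 1, so under these assumptions the shift always favours the pump. As a check with whole numbers, take 100 Group B patients with 50 deaths, 5 of them before insertion. Removing those leaves 45/95 = 47.4%, against 50% in Group A.

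| Assumed m | d = 1% | d = 2% | d = 5% |
|---|---|---|---|
| 30% | 29.3% (0.7 points) | 28.6% (1.4) | 26.3% (3.7) |
| 50% | 49.5% (0.5) | 49.0% (1.0) | 47.4% (2.6) |
| 70% | 69.7% (0.3) | 69.4% (0.6) | 68.4% (1.6) |

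Entries are observed Group B mortality, with the spurious benefit in brackets.

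**Effect on false positives.** Assume further 100 patients randomised per arm, m = 50%, a two-sided 5% test and a normal approximation:

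- SE = √[m(1 − m)/100 + B(1 − B)/(100(1 − d))], where B is observed Group B mortality
- Shift/SE = 0.071, 0.144 and 0.368 for d = 1%, 2% and 5%
- Chance of a significant result favouring the pump = Φ(−1.96 + shift/SE) = 2.95%, 3.47% and 5.56%, against 2.5% with no removal

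**If controls could also be removed.** With a share d_A removed from Group A on the same ground and d_B from Group B, the spurious benefit is (1 − m)[d_B/(1 − d_B) − d_A/(1 − d_A)]. It is zero when the shares are equal and reverses when d_A is larger. The one-way result therefore depends on controls having no planned insertion.

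**With all randomised patients analysed.** Both arms show m and the spurious benefit is 0.

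**The case against.** The strongest reply is that the protocol nowhere says withdrawn patients are left out of the analysis. A reader might infer that the list, followed literally, deletes Group B deaths. The text does not go that far. It speaks of withdrawal or discontinuation, not of excluding or replacing patients, and the in-hospital outcome of someone who has died is already known.

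There is also a harmless reading. Procedures item 5 repeats the blood sampling at hour 6 or one hour after insertion, and a patient who dies before insertion cannot give the post-insertion sample. Item 1 may mean only that study procedures end. This stands as a possible meaning. It does not close the gap, because nothing in the plan says that the death is then counted. Monitoring throughout the hospital stay is a follow-up rule, not an analysis rule.

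A second reply is that confinement to Group B is inferred. Control care is not described, and since the strategy under test is early insertion, later pump use in controls is not expressly ruled out. That also stands. No such insertion is described, so Group B alone is the natural reading, but the direction of bias is conditional on it.

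Third, the window is short and the numbers may be small. At 1% to 2% removed, the table shows shifts of 0.3 to 1.4 points. The documents do not support assuming a large share.

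Finally, items 3 and 4 read naturally as safety reasons to stop the pump. The documents do not show that those patients would be dropped, nor which way the result would move if they were.

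**Conclusion.** The concern holds as a conditional one. The plan lists a primary-outcome event as a ground for withdrawal or discontinuation and does not say that the event is counted. If such patients are removed from the analysis and controls receive no pump, mortality is biased toward the pump by (1 − m)d/(1 − d). That is 0.5 to 2.6 points at an assumed 50% mortality with 1% to 5% removed, and 0.3 to 3.7 points over the whole grid of assumed values. The true size cannot be known from the documents. If every randomised patient is analysed, this bias does not arise.

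It would go too far to conclude that the plan excludes these deaths or that the trial's result is biased. The defect is a rule open to a biasing reading, with no analysis population to settle it. It should be fixed because it touches the primary comparison and the remedy is cheap. Confidence is medium: the text is clear about what is listed and silent about what follows.

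**What to change.** 1. In Withdrawal or Discontinuation Criteria, remove item 1. State that items 3 and 4 are reasons to stop the pump only, with follow-up continuing.
2. In Analysis Method, add: *In-hospital mortality is analysed in all randomised patients by allocated group, whatever criterion is met. Deaths before insertion are counted. Patients whose family ends treatment are followed to discharge or death unless permission to use data is withdrawn.*

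The second change removes the bias by itself; the first stops the list from contradicting it. The cost is protocol wording, with no extra patients or procedures. The downside is that patients who never receive the pump, or have it stopped early, stay in Group B. This may dilute a true device effect and make the mortality estimate less favourable to the pump. The clinical thresholds for stopping the pump remain for the investigators.

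### The plan does not say whether deaths after family-requested termination of treatment count toward in-hospital mortality; on a natural reading of the withdrawal list they would be lost

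*Combined protocol and SAP*

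**What the plan says.** The combined protocol and SAP has one undivided list of four items headed "Withdrawal or Discontinuation Criteria". Item 1 is "Patient dies prior to intra aortic balloon pump insertion" and item 2 is "Treatment termination requested by family". Items 3 and 4 concern a fall in haemoglobin from bleeding and a low ankle brachial index. The list does not say which items end study participation and which only stop the intervention. Nor does it define what treatment means in item 2.

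The primary outcome is "In-hospital mortality". On follow-up, Procedures item 6 says only "Research subjects will be monitored during hospitalization". Procedures item 2 says "Research subjects were then randomized into two groups": a control group, and a group that receives the balloon pump (IABP) within 3 hours of return of spontaneous circulation. Neither blinding nor a sham procedure is described.

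Analysis Method opens with "Data analysis using SPSS 20.0 software program with appropriate statistical test" and goes on to name tests by variable type. It gives no analysis set, no intention-to-treat rule and no handling of withdrawn patients.

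**The concern.** In survivors of cardiac arrest, a family's request to stop treatment is plausibly related to how the patient is doing, and therefore to the primary outcome. If such patients leave the study, the trial loses outcomes selectively. It would then report mortality among patients whose families made no such request, which is a different quantity from in-hospital mortality in everyone randomized.

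The comparison between arms is also exposed. One arm receives an invasive device and the other does not, with no concealment described, so families and clinicians may well know the allocation. If requests are more frequent in one arm, more deaths are removed from that arm and its mortality looks lower than it is. None of the tests named in Analysis Method corrects for this. A list that leaves the matter open also allows patients to be excluded after their outcome is known.

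**Working it through.** **1. What the text settles.** The documents state no sample size, mortality rate, effect size or expected withdrawal rate, so there is no planned figure to reproduce. The first step is to read the sections together.

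- Item 1 of the list is a death before insertion. A patient who dies before insertion has no device to discontinue, so item 1 makes sense only as removal from the study. Nothing in the list separates item 2 from item 1.
- Items 3 and 4 can be read as reasons to stop the device, which is the other half of the heading.
- Procedures item 6 sets monitoring during the stay without exceptions. It does not say that a withdrawn patient remains a research subject, or that a monitored patient enters the analysis.
- Analysis Method does not resolve the question either way.

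The text therefore neither excludes nor includes these deaths, and removal is a natural reading.

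**2. What removal would do (all rates assumed).** Let an arm have n patients and D true deaths. Let d patients be dropped, all of whom die. Observed mortality is (D − d)/(n − d). Take n = 100 and D = 50 in each arm, so the true difference is zero.

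| Dropped, IABP vs control | IABP | Control | IABP minus control |
|---|---|---|---|
| 20 vs 10 | 30/80 = 37.5% | 40/90 = 44.4% | −6.9 points |
| 10 vs 20 | 40/90 = 44.4% | 30/80 = 37.5% | +6.9 points |
| 15 vs 10 | 35/85 = 41.2% | 40/90 = 44.4% | −3.3 points |
| 20 vs 20 | 30/80 = 37.5% | 30/80 = 37.5% | 0 |

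The first row means that 20/50 = 40% of IABP deaths and 10/50 = 20% of control deaths are dropped.

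**3. Other assumed mortality rates.** Let p be true mortality and w the share of an arm's deaths that is dropped. Observed mortality is p(1 − w)/(1 − pw). With w = 10% in one arm and 30% in the other:

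- p = 40%: 0.36/0.96 = 37.5% vs 0.28/0.88 = 31.8%, a false difference of 5.7 points.
- p = 50%: 0.45/0.95 = 47.4% vs 0.35/0.85 = 41.2%, 6.2 points.
- p = 60%: 0.54/0.94 = 57.4% vs 0.42/0.82 = 51.2%, 6.2 points.

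The arm with more dropped deaths looks better each time.

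**4. If there is a real effect.** Assume true mortality of 50% (control) and 35% (IABP), a 15.0-point difference.

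- 30% of control and 10% of IABP deaths dropped: 41.2% vs 0.315/0.965 = 32.6%, 8.5 points.
- 10% of control and 30% of IABP deaths dropped: 47.4% vs 0.245/0.895 = 27.4%, 20.0 points.
- Equal shares: 14.7 points at 10% and 13.8 points at 30%.

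**5. Where the bias vanishes.** If dropped patients die at the same rate as the rest, nothing is distorted: 20 dropped with 10 deaths among them gives (50 − 10)/(100 − 20) = 40/80 = 50%. The bias depends on requests being linked to death.

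**The case against.** A reader might infer that the plan removes these patients and does not count their deaths. The documents do not say so. The heading also covers discontinuation, and items 3 and 4 fit that sense. Procedures item 6 has no exception for patients who stop treatment. Read with the primary outcome, it favours counting the death.

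Treatment is also undefined in item 2. Procedures calls Group B the treatment group, so the item could mean a family asking only for the IABP to be stopped. It would then concern one arm and would not imply that death follows. It is equally an inference that item 2 applies in both arms throughout the stay, that requests usually come when the outlook is hopeless, and that the trial is open. These are plausible, but the documents state none of them.

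The illustration shows only that bias is possible. Its direction is arbitrary, and equal loss with equal true mortality produces no false difference. Finally, the root gap is the missing analysis set, and one rule would cover all four items.

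All of this stands as a limit on how strongly the point can be put. It does not remove the point. Item 1 supports the removal reading, monitoring is not an analysis rule, and no sentence protects the primary outcome from losing these deaths.

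**Conclusion.** The concern holds as an unresolved rule on the primary outcome; an exclusion of these deaths is not established. The plan does not say whether a death after a family request counts, and on a natural reading of the list it would not. Applied that way, the list drops patients after randomization for a reason plausibly linked to prognosis, and could bias the mortality comparison in either direction.

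Under the assumed rates above, the false difference is about 3 to 7 points when true mortality is equal, and an assumed 15.0-point effect could appear as anything from 8.5 to 20.0 points. These sizes rest on three assumptions: the patients are removed from numerator and denominator, all of them die, and the dropped share differs by arm as chosen. None of the rates comes from the documents. The matter should be settled before analysis because it can determine the primary result.

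**What to change.** In Withdrawal or Discontinuation Criteria, separate discontinuation of the intervention from withdrawal from the study. Define what treatment means in item 2. State that a family's request to end treatment is not by itself a reason to leave the study or the analysis.

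In Analysis Method, state that every randomized patient is analysed in the assigned group, and that vital status at hospital discharge is collected unless further data collection is explicitly refused. Record each family-requested termination, with its date and reason, and report the numbers by arm beside the primary result.

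The cost is a few sentences and a small addition to the case report form. Reported mortality may be higher than if these patients were left out. Nothing here takes a position on when treatment should be stopped.
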